2.3 EFFICACY/SAFETY MEASURES AND ENDPOINTS

2.3.1 PRIMARY ENDPOINT

The primary endpoint for this study is the percentage change in target ulcer area over the 12-week treatment period. Target ulcer area is defined as surface area as measured by the ARANZ Silhouette Device at each study visit by the Investigator.

The percentage change in target ulcer area over the 12-week treatment period is

Document Number: 1004313

Document Part: 000

Document Version: 06

Document Status: Released

then derived using the baseline area and the area recorded at Study Visit 13. In cases where the target ulcer area is closed in the opinion of the Investigator (regardless of 1-week confirmation), the ulcer area will be imputed as 0 cm². In circumstances where the ulcer area is missing at the Study Visit 13 for subjects that have not withdrawn prematurely due to closure, the last observation carried forward (LOCF) method will be used.

2.3.2 SECONDARY ENDPOINTS

The KEY SECONDARY endpoints are the percentage change in the target ulcer dimensions not assessed as part of the primary endpoint, namely depth and volume. As defined for the primary endpoint, ulcer depth and volume will be measured by the ARANZ Silhouette Device at each visit by the Investigator, and the percentage change in depth over the 12-week treatment period will be derived using the baseline depth and the depth recorded at Study Visit 13. The endpoint will be repeated for ulcer volume.

The remaining secondary endpoints are detailed below:

- The proportion of subjects with confirmed ulcer closure (achieved by surgical intervention or secondary intention) during the 12-week treatment period. The subject's ulcer closure status (open or closed) will be assessed by the Investigator at each study visit. Complete wound closure is defined as complete re-epithelialization, without drainage or the need for a dressing, confirmed at one-week post initial ulcer closure.
When an ulcer closure is initially observed at a weekly treatment visit from Visits 2 to 13, it will be confirmed at the one further study assessment one week later (Visit 14) so that it can be considered as a complete wound closure.
- The time in days to (confirmed) ulcer closure during the 12-week treatment period (with confirmed closure as defined in the previous paragraph). Once a subject has achieved confirmed ulcer closure, either by surgical intervention or secondary intention, the time to healing will be calculated as the number of days between the date of the randomization visit (Study Visit 1) and the date

ST:

9 7 5

Reference:

CE/052/PIC

Customer Code:

0 5

at which ulcer closure first occurred. For those subjects who drop out or who do not achieve the complete wound closure during the 12-week treatment period, the time to complete wound closure will be considered as censored at the last visit date (censored date) of the treatment period or 84 days (i.e. 12 weeks x 7 days), whichever occurs earlier.

- The difference between treatments in the change in subject reported Quality of Life (QoL) during the 12-week treatment period. The Health related Quality of Life (HRQoL) will be assessed using the EQ-5D and Cardiff Wound Impact Schedule (CWIS) validated instruments.

The EQ-5D is a standardized measure of health status developed by the EuroQol Group and provides a simple measure of general health. The EQ-5D descriptive system contains 5 dimensions: mobility, self-care, usual activities, pain/discomfort and anxiety/depression. The subject is asked to state each dimension on a scale comprising of 5 levels: no problems, slight problems, moderate problems, severe problems, and extreme problems. This decision results in a 1-digit number expressing the level selected for that dimension. The digits for 5 dimensions can be combined in a 5-digit number describing the respondent's health state. Separately, the EQ-5D visual analog scale (EQ VAS) records the subject's self-rated health on a vertical, Visual Analog Scale (VAS). This information is used as a quantitative measure of health outcome. In comparison, the CWIS is a measure designed to specifically assess the impact of lower limb chronic wounds on subject health-related quality of life (HRQoL) and activities of daily living (ADL). The CWIS contains four domains; Quality of life, Well-being, Physical symptoms and Daily Living (Experienced and Stressfulness of experience are two separate domains).

Both the EQ-5D and CWIS will be provided to all subjects participating in the study at the Randomization Study Visit 1 and at the End of Treatment period for completion. Missing and ambiguous values will be coded as per the relevant instrument documentation.

Document Number: 1004313

Document Version: 06

Document Part: 000

Document Status: Released

The Cardiff Wound Impact Schedule (CWIS) is a condition-specific quality of life tool that has been developed at the Wound Healing Research Unit in Cardiff. The tool has undergone extensive piloting to establish the psychometric properties of the tool. The tool gives a profile of scores for Well-Being, Physical Symptoms and Daily Living and Social Life. Physical Symptoms and Daily Living, and Social Life are assessed for both the experience of a given symptom and the associated stress experienced by the individual. In addition, an indication of overall HRQoL is assessed using a global scale, together with an indication of the satisfaction with that HRQoL.

Study subjects will complete both instruments at the Randomization Study Visit 1 and at the End of Treatment period. Scoring/coding of responses, and the change in continuous measures of the EQ-5D and CWIS instruments (including Time Trade-off (TTO) index, EQ-VAS, and domain averages) between the Randomization/Study Visit 1 and End of Treatment will be calculated according to the suppliers validated instructions.

2.3.3 EXPLORATORY ENDPOINTS

The exploratory endpoints are as follows:

Assessment of change in target ulcer progression parameters over the 12-weeks and comparison between treatments including: Estimation of the types of tissue present on the target ulcer, Presence of Infection/Clinical signs of infection, Condition of peri-wound skin, Need for administration of antibiotics and additional interventions, dressing wear time, pain on removal of dressing and at initiation of, and during, therapy.

- The subject's target ulcer will be assessed by the Investigator at each study visit. Where possible this assessment will be made using a modified Bates-Jensen wound assessment tool, this will include information concerning presence of Undermining, Necrotic Tissue Type and Amount, Exudate Type and Amount, Granulation Tissue and Epithelialization. Otherwise the Investigator's assessment against a custom descriptive scale will be used.

Document Number:	1004313	Document Part:	000
Document Version:	06	Document Status:	Released

ST:

9

7

5

Reference:

CE/052/PIC

Customer Code:

0

5

- Condition of peri-wound skin will be assessed by the Investigator against a custom 7-category descriptive scale: Normal, Erythematous, Edematous, Eczematous, Excoriated, Macerated and Indurated. Presence of each skin type will be recorded.
- Assessment of the presence of infection and clinical signs of infection will be undertaken by the Investigator.
- Presence of Undermining, Necrotic Tissue Type and Amount, Exudate Type and Amount, Granulation Tissue and Epithelialization will be assessed using the modified Bates Jensen wound assessment tool.
- Pain associated with removal of dressing, and at initiation of, and during, therapy will be assessed using the Pain VAS scale.
- The need for administration of antibiotics and additional interventions in the opinion of the Investigator will be recorded.
- The duration of dressing wear (dressing wear time) will be calculated using the visit date captured on the CRF and, if applicable, the date of additional/unscheduled dressing changes; by subtracting the date of dressing application from the date of dressing removal. The average wear time will then be derived for each subject using the sum of duration of wear for the subject and the number of dressings utilized by the subject.

2.3.4 SAFETY ENDPOINTS

Adverse events are recorded at each visit. Vital signs (blood pressure and pulse) are measured at Screening.

Routine laboratory tests are conducted at Screening to confirm eligibility. Laboratory tests are analyzed by a central laboratory and include the following parameters:

Document Number: 1004313
Document Version: 06

Document Part: 000
Document Status: Released

ST:

9 7 5

Reference:

CE/052/PIC

Customer Code:

0 5

Hematology: Red Blood Cell (RBC) count, Hemoglobin, Hematocrit, Platelets, White Blood Cell (WBC) total count, and differential (%) including absolute counts (x 10⁹/L)

Blood Biochemistries: Sodium, Potassium, Calcium, Creatinine, Total Bilirubin, ALT, AST, Alkaline Phosphatase, Albumin, Total Protein, Urea, Glucose, and HbA1c

Additional Chemistries: Pre-albumin

2.3.5 HANDLING OF MISSING, INCOMPLETE, AND REPEAT DATA

The handling of missing data and/or missing planned visits is described in the following section for the primary endpoint and secondary endpoints.

Percentage change in ulcer Area – Primary Endpoint:

The percentage change in target ulcer area over the 12-week treatment period is derived using the baseline area and the area recorded at Study Visit 13. Missing values and/or visits may occur at these visits if data is not collected or a subject discontinues from the treatment due to wound closure or early termination. In cases where the target ulcer area is missing or an ARANZ image cannot be taken due to the ulcer being closed in the opinion of the Investigator, the ulcer area at the Study Visit will be imputed as 0 cm².

In circumstances where the ulcer area is missing at the Study Visit 13 for subjects that have not withdrawn prematurely due to closure, the last observation carried forward (LOCF) method will be used.

Percentage change in ulcer Depth/Volume – Key Secondary Endpoint:

The methods detailed above for the handling of missing/incomplete data regarding the primary endpoint will also be used for Depth and Volume.

Proportion of subjects with confirmed ulcer closure – Secondary Endpoint:

The subject's ulcer closure status (open or closed) will be assessed by the Investigator at each study visit. Closure is confirmed at one-week post initial ulcer closure. Missing values and/or visits may occur at these visits if data is not collected at the Study Visit, or a subject discontinues from the treatment due to wound closure or early termination. Missing data may also exist if the one-week closure

Document Number: 1004313
Document Version: 06

Document Part: 000
Document Status: Released

ST:

9 7 5

Reference:

CE/052/PIC

Customer Code:

0 5

confirmation visit is not attended. In cases where the ulcer closure status is missing at a Study Visit or the subject is withdrawn from the study, the Last Observation Carried Forward (LOCF) method will be used (with the exception of the confirmatory period).

In addition, two separate sensitivity derivations will be performed to account for missing data:

- Worst case: In cases where subjects had missing data over the confirmatory target ulcer closure period (1 week follow-up) and it is unknown whether the closure is confirmed, these will be imputed as: Confirmed Closure=No.
- Best case: In cases where subjects withdraw from the study prior to the end of the 12-week treatment period (except in cases where the ulcer has closed), the following will be imputed: Confirmed Closure=Yes.

Time to achieve complete closure – Secondary Endpoint:

Once a subject achieves complete ulcer closure as defined above, the time to complete ulcer closure will be calculated as the time interval in number of days between the date of randomization (i.e. Study Visit 1) and the date of the initial observation of the wound ulcer closure. For those subjects who drop out or who do not achieve the complete wound closure during the 12-week treatment period, the time to complete wound closure will be considered being censored at the last visit date (censored date) of the treatment period (i.e. from Study Visits 2 to 13) or 84 days (i.e., 7 days x 12 weeks), whichever occurs earlier. There is no missing data for time to achieve complete closure.

Difference between treatments in Health Related Quality of Life (HRQoL) – Secondary Endpoint:

The EQ-5D and CWIS instruments will be completed at Randomisation (Study Visit 1) and End of treatment. Missing data can occur with the questionnaires due to missed questions or the subject being unwilling to answer. Missed visits may also cause missing data. In cases where questions are skipped, the missing responses will be coded as per the instrument guidelines. Separately, in cases where there are missing individual responses (not complete missing questionnaires) contained on the end of treatment questionnaire, these will be coded as the Last Observation Carried Forward (LOCF) from the baseline questionnaire.

Document Number: 1004313
Document Version: 06

Document Part: 000
Document Status: Released

Ulcer progression parameters – Exploratory Endpoint:

Assessment of change in target ulcer progression parameters over the 12-weeks and comparison between treatments including: Estimation of the types of tissue present on the target ulcer, Presence of Infection/Clinical signs of infection, Condition of peri-wound skin, Need for administration of antibiotics and additional interventions, dressing wear time, pain on removal of dressing and at initiation of, and during, therapy. Missing values and/or visits may occur at these visits if data is not collected or a subject discontinues from the treatment due to ulcer closure or early termination.

In cases where the ulcer is recorded as closed in the investigators opinion the following imputations will be made at the corresponding Study Visit to account for the missing values recorded:

- Presence of infection = No
- Presence of clinical signs of infection = No
- Level of Exudate = None/No
- Extent of undermining = None
- Necrotic tissue present = No
- Epithelialization at target ulcer = 100% wound covered, surface intact

Remaining values which are required to be analysed at the end of the 12-week treatment period will utilize the Last Observation Carried Forward (LOCF) method for the last non-missing post-baseline Study Visit.

In cases where dressing wear time cannot be calculated for a single dressing (for example, loss to follow up with no removal assessment recorded), the average wear time for the subject will be calculated for the trial duration up to (and excluding) the dressing with unknown duration of wear.

Safety Endpoints:

Any resultant incomplete or missing data of vital signs or safety parameters will be treated as missing in the statistical analyses involving these parameters.

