9.2 DISCONTINUED SUBJECTS

Discontinued subjects are those who voluntarily discontinue participation, who are withdrawn for safety reasons or who have missed a sufficient number of study visits, procedures or test article doses, as defined below, to be ineligible for further participation.

All subjects who discontinue the study prior to completing the regularly scheduled visits should complete the End of Treatment Assessment or Early Discontinuation Visit 14.

Any changes in medical health and/or the use of concomitant medications will be captured. If any SAE, target ulcer AE, or DevD were observed since the previous visit, they must be recorded (refer to Section 12, *Adverse Events*, for instructions on reporting and evaluation

procedures). All females of child-bearing potential must also undergo a urine pregnancy test upon exiting the study. Finally, if appropriate, the Investigator will also advise the subject of subsequent therapy and/or procedures necessary for their medical condition.

During the course of the study, the subject must be discontinued from study treatment in the case of any of the following:

- An infection of the target ulcer occurs and does not respond as expected to appropriate conventional treatment after 2 weeks of therapy
- Progressive disease defined by an increase of $\geq 75\%$ in the ulcer surface area at any time during the treatment phase using the measurement from Run-in Visit 2 as the baseline target ulcer measurement. The increase is calculated as follows:

$$\left[\left(\frac{Area_{V_n} - Area_{RV2}}{Area_{RV2}} \right) \times 100 \right] \geq 75$$

- Persistence of an SAE, device –related AE or abnormal laboratory value that in the opinion of the Investigator places the subject at risk should they continue in the study
- Subject misses > 2 weekly study visits during the treatment period.
- Subject misses 14 consecutive days of therapy or standard care treatment during the treatment period
- Subject misses 21 cumulative days of therapy during the treatment period

Subjects may be discontinued from the study at any time if, in the opinion of the Investigator, their continued participation in the study poses a risk to the subject. Additionally, subjects may be discontinued from the study for the following reasons:

- Adverse device effects
- Lost to follow-up
- Subject decision unrelated to an adverse device effects
- Noncompliance (e.g., did not follow instructions, took disallowed medications)
- Other

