- Ulcer Closed/Ready for surgical closure =Yes at last attended Study Visit i, Ulcer Closed=missing at Follow up assessment (Visit 14). Confirmed Closure = missing
- Ulcer Closed/Ready for surgical closure =No at last attended Study Visit i. Confirmed Closure = No

In cases where the ulcer closure status is missing at a Study Visit, the Last Observation Carried Forward (LOCF) method will be used.

21. The derivation for whether confirmed ulcer closure was achieved will be repeated to form two further separate variables, with the exceptions below:

- i. In cases where subjects had missing data over the confirmatory target ulcer closure period (1 week follow-up) and it is unknown whether the closure is confirmed, these will be imputed as: Confirmed Closure=No. All remaining scenarios will be derived as described in the previous derived variable.
- ii. In cases where subjects withdraw from the study prior to the end of the 12-week treatment period (except in cases where the ulcer has closed), the following will be imputed: Confirmed Closure=Yes. All remaining scenarios will be derived as described in the previous derived variable.

22. The components of the CWIS will be derived as follows at baseline and end of treatment.

a) Physical symptoms and daily living

Each individual response will be coded by the following formulae:

Document Number:	1004313	Document Part:	000
Document Version:	06	Document Status:	Released

ST:

9

7

5

Reference:

CE/052/PIC

Customer Code:

0

5

Not at all/Not applicable – 5

Seldom/Slightly – 4

Sometimes/Moderately – 3

Frequently/Quite a bit – 2

Always/Very – 1

An overall score for this domain will then be calculated as the sum of the 24 individual values (12 individual values each for experience and stress related measures).

The overall score will then be transformed onto a scale of 0-100 using the following formula:

$$[(\text{Overall actual score (sum of 24 individual scores)} - \text{minimum possible score}) / \text{range of possible scores}] * 100$$

If all 24 questions are completed, the minimum value =24 and the range of scores = (120 - 24) = 96

b) Social Life

Each individual response will be coded by the following formulae:

Not at all/Not applicable – 5

Seldom/Slightly – 4

Sometimes/Moderately – 3

Frequently/Quite a bit – 2

Always/Very – 1

An overall score for this domain will then be calculated as the sum of the 14 individual values (7 individual values each for experience and stress related measures).

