In addition, a sensitivity analysis will be performed to ensure that the efficacy findings are not reliant on assumptions made in either the analysis or derivations. For purposes of the sensitivity analysis, the time to confirmed closure for those subjects discontinuing the treatment period prematurely, will be censored at the maximum possible duration of treatment under the study protocol (84 days), rather than time of actual discontinuation. Lastly, the two sensitivity analyses defined in the proportion of subjects achieving confirmed closure analysis will be repeated for the time to confirmed closure, in these cases the censoring flag may be modified as detailed previously, but the time in days will remain unchanged.

Change in subject reported Quality of Life (QoL)

The instruments used to assess subject reported Quality of Life will be the Cardiff Wound Impact Schedule (CWIS) and the EQ-5D. All analyses relating to Quality of Life assessments will be performed using the Full Analysis Set.

Cardiff Wound Impact Schedule

The parameters for each of the domains of the CWIS questionnaire (Wellbeing, Physical symptoms and daily living, Social life) in addition to Overall HRQoL and Patient Satisfaction with overall HRQoL at baseline and end of treatment will be summarized using frequency distributions which will detail the number and percentage of subjects which fall into each category. The change in the CWIS score for each of the domains between baseline and end of treatment will be summarized.

A two sample t-test will be used to test for a difference in the mean change in CWIS score between treatments for each of the domains separately. 95% confidence intervals will also be presented. If the assumptions of the t-test are violated, the Wilcoxon rank sum test will be used instead with Hodges-Lehmann estimates of the median difference and 95% confidence interval reported.

As a sensitivity analysis, the above analysis will be repeated with any missing values coded using LOCF.

EQ-5D

Subject responses to the EQ VAS scale and derived Time Trade-off (TTO) indexes and domain averages at each assessment are continuous variables and will be summarized.

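### The best-case closure sensitivity analysis counts every early withdrawal with an open ulcer as healed in both arms, so unequal withdrawal shifts the comparison towards the arm that loses more subjects

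*SAP*

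**What the plan says.** **Best case.** SAP 2.3.5 reads "Best case: In cases where subjects withdraw from the study prior to the end of the 12-week treatment period" and continues "except in cases where the ulcer has closed), the following will be imputed: Confirmed Closure=Yes". Derived variable 21(ii) in SAP 4.3 repeats the rule and leaves everything else alone: "Confirmed Closure=Yes. All remaining scenarios will be derived as described in the previous derived variable". SAP 4.10 and protocol 10.3.2 carry the same rule, for the Full Analysis Set. None of the four places limits it by arm or by reason for leaving.

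**Worst case.** This variant changes only closures whose one-week check is missing: where "it is unknown whether the closure is confirmed, these will be imputed as: Confirmed Closure=No".

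**Main analysis.** For a missing closure status "or the subject is withdrawn from the study, the Last Observation Carried Forward (LOCF) method will be used". A subject who leaves with an open ulcer is therefore not closed (also derived variable 20, SAP 4.3).

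**Time to closure.** Both variants are repeated in the proportional-hazards analysis, where "the censoring flag may be modified as detailed previously, but the time in days will remain unchanged" (SAP 4.10; likewise protocol 10.3.2). A separate sensitivity analysis censors premature discontinuations at 84 days.

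**Who leaves early.** Protocol 9.2 states: "During the course of the study, the subject must be discontinued from study treatment in the case of any of the following". The list includes "Progressive disease defined by an increase of" at least 75% in ulcer area over Run-in Visit 2, and a target-ulcer infection that has not responded after two weeks. Those who discontinue early go to Visit 14, which SAP 2.1 makes the termination visit. Protocol 9.1.6 has ulcers that are still open measured there.

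**The concern.** The stated aim of the sensitivity analyses is to show that the efficacy findings do not hang on assumptions. For dropout, the best-case rule cannot show this, for three reasons.

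- It overrides known outcomes. A subject whose enlarging ulcer has just been measured at the exit visit is recoded as healed.
- It treats both arms alike. What it adds to each arm is that arm's withdrawal proportion, which is not a measure of healing.
- The worst case acts on different subjects, those with a missing confirmation. The two variants are therefore not opposite ends of one range, and together they do not bracket what dropout could do to the comparison.

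The trial is open-label. The reasons for leaving in protocol 9.2 include device effects, missed therapy days and subject decision, and these could differ between two devices of different size and handling. Unequal withdrawal is therefore possible. If it occurs, a report could present a difference in withdrawal as support for a difference in healing.

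**Working it through.** **The plan's own figures.** The documents give no closure rate and no figure for this sensitivity analysis. The figures that limit its effect are in SAP 3.1: 128 completers, 20% dropout, 160 randomized, 80 per arm. Check: 128 / (1 − 0.20) = 160, which agrees. Expected withdrawals: 0.20 × 160 = 32.

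**Assumptions.** All 160 subjects are in the Full Analysis Set. All 32 withdrawals have open ulcers. The closure rates and the split of withdrawals by arm are chosen for illustration. The calculation is unadjusted, whereas the planned model is a covariate-adjusted logistic regression.

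**Formula.** With n subjects per arm, let x be the closures under the main LOCF rule and w the early withdrawals with open ulcers. The best-case proportion in an arm is (x + w)/n. The difference between arms is therefore

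(x₁ − x₂)/n + (w₁ − w₂)/n,

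that is, the main difference plus the difference in withdrawal proportions.

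**Equal closure, 32/80 (40%) in each arm under LOCF:**

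| Withdrawals, arm 1 / arm 2 | Best-case closure | Shift in points (95% CI) | p | Odds ratio |
|---|---|---|---|---|
| 16 / 16 | 48/80 = 60% vs 48/80 = 60% | 0 (−15.2 to 15.2) | 1.00 | 1.00 |
| 20 / 12 | 52/80 = 65% vs 44/80 = 55% | +10 (−5.1 to 25.1) | 0.20 | 1.52 |
| 24 / 8 | 56/80 = 70% vs 40/80 = 50% | +20 (5.1 to 34.9) | 0.010 | 2.33 |

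For the 24/8 row, the pooled proportion is 96/160 = 0.60, the standard error √(0.60 × 0.40 × 2/80) = 0.0775, and z = 0.20/0.0775 = 2.58. The odds ratio is (0.70/0.30)/(0.50/0.50) = 2.33. With 30% or 50% closure in both arms, the 24/8 shift is again 20 points (p = 0.011 and 0.006).

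**A case where the sign changes.** Let LOCF closure be 24/80 vs 32/80, a difference of 30% − 40% = −10 points, with withdrawals 24 vs 8.

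- Planned best case: 48/80 vs 40/80, 60% − 50% = +10 points.
- Arm 1 withdrawals No, arm 2 Yes: 24/80 vs 40/80, 30% − 50% = −20 points (95% CI −34.9 to −5.1).
- Arm 1 withdrawals Yes, arm 2 No: 48/80 vs 32/80, 60% − 40% = +20 points (95% CI 4.8 to 35.2).

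The planned rule reports one value inside a range of −20 to +20 and does not show the range.

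**Equal withdrawal.** With 40% closure in both arms and a 16/16 split, the planned rule gives 0. The arm-specific extremes give 32/80 vs 48/80 (−20 points) and 48/80 vs 32/80 (+20 points). A zero shift under the planned rule is thus not evidence that dropout is harmless.

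**Effect of keeping documented failures as No.** If k of the w withdrawals in an arm are documented failures, the extremes run from (x₁ − x₂ − (w₂ − k₂))/n to (x₁ − x₂ + (w₁ − k₁))/n. The ranges above have k = 0 and are the widest; each documented failure narrows them.

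**Time to closure.** Derived variable 19 sets the time for an early withdrawal at the last visit attended. If the flag is switched to closure and the time left as it is, a subject whose last visit, with a growing ulcer, is at day 21 becomes a healing event at day 21.

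**The case against.** The strongest reply is that the plan already contains the conservative result. LOCF makes open-ulcer withdrawals non-closures in the main analysis. The variant is openly labelled as a best case and reported beside that result, and no decision rule depends on it. For time to closure, the 84-day censoring analysis is already planned. All of this stands, and it limits the point to one variant of two secondary endpoints.

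A reader might also infer more than the documents support:

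- *That the arm with more treatment failures will look better.* Failures who stay to week 12 with an open ulcer remain not closed. Only early withdrawal counts, and only if it differs between arms.
- *That growth and infection cases are certainly covered.* Protocol 9.2 speaks of stopping study treatment, the imputation rule of leaving the study. Exit at Visit 14, with no later follow-up described, makes overlap likely, but neither document says so.
- *That early failures will be coded as healing events.* The SAP says the flag may be modified, so the text allows this without committing to it.
- *That the trial's effect will be reversed.* This needs a withdrawal imbalance larger than the LOCF difference and in the opposite direction. The documents give only 20% dropout overall, with no split by arm.

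Arm-specific extremes may also be too wide to settle anything. That is a fair limit on how informative they are. It is not a reason to report instead a single value that conceals the range.

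**Conclusion.** The concern holds in this limited form. The best-case rule recodes every early withdrawal with an open ulcer as healed, in both arms and whatever the reason. It moves the closure difference by the between-arm difference in early-withdrawal proportions, towards the arm losing more subjects. With 80 per arm and 32 withdrawals, that is 0, 10 or 20 points for splits of 16/16, 20/12 or 24/8. The total of 32 follows from the plan's dropout allowance; the splits and closure rates are assumptions. Paired with a worst case that acts on other subjects, the rule does not bracket the effect of dropout. The main closure analysis and the primary and key secondary endpoints are untouched, so this is a cheap improvement to a sensitivity analysis and not a threat to the trial's main conclusion.

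**What to change.** Make the change in SAP 2.3.5, 4.3 (variable 21(ii)) and 4.10 and in protocol 10.3.2 together, so that the documents stay aligned.

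1. Replace the uniform best case with two arm-specific extremes: PICO withdrawals No with tNPWT withdrawals Yes, and the reverse.
2. In every variant, keep as No any subject with a documented open ulcer who discontinued for area growth or non-responding infection. In the time analysis keep these subjects censored at 84 days, as in the existing sensitivity analysis.
3. State whether the rule covers subjects who stop study treatment, those who leave the study, or both, and whether the censoring flag will be changed.
4. Keep the missing-confirmation variant, but describe it as addressing unconfirmed closures and not as the counterpart of the dropout variants.

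No new data are needed: ulcer status is assessed at Visit 14, and SAP 4.5 already summarizes reasons for withdrawal. The cost is a few extra logistic and proportional-hazards runs, and bounds that will be wider and may be inconclusive.
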